9.3 End of trial

The end of the trial will be 31st December 2016, or earlier if the biological studies are completed before then. At this point the 'declaration of end of trial' form will be submitted to the MHRA and REC.

9.4 Assessment flowchart

	Pre Reg	Wk 1	Wk	post	Mon	ths aft	er end	CRT												
	Therkey	VVKI	2	3	4	5	6	7	8	9	10	11	12	13	14	ор	6	12	24	36
Radiotherapy								•												L
E Cetuximab								•												
E Capecitabine								•												
≝_ Irinotecan							→													
Surgery															X					
Physical exam	X																X	X	Х	X
Vital signs	X	X	X	X	X	X	X													
Height & weight	X																			
g WHO	X																			
Capecitabine compliance			X	Х	X	X	X													
FBC	X	X	X	X	X	Х	X	X	X	X	Х									
. Clotting profile	X																			
U+E+creat	X	X	X	X	X	Х	X	X	X	X	Х									
ਚੁੱ Magnesium	X	X	X	Х	X	Х	Х	Х	X	X	Х	Х	Х	Х	Х					
	X	X	X	X	Х	Х	X													
S LFT	Х	Х	X	Х	X	Х	X	Х	Х	Х	Х									
E Histological confirmation	Х																			
CEA CEA	Х												X							
Liver (US or CT)	Х																			
A MRI pelvis	X												X							
CXR	X																			
Toxicity	X	X	X	X	X	Х	X	X	X	X	Х						Х	Х	Х	X
Consent form	X																			
Collection of diagnostic tissue block for KRAS testing																				
Ancillary study blood samples x 2 (optional)	X																			
Registration/baseline CRF	X																			
는 Copy of baseline MRI	X																			
E Treatment CRF		X	X	Х	X	Х	X	Х	X	X	Х									
Post treatment summary CRF													X							
Copy of post CRT MRI report													X							
g Surgery CRF																X				
Copy of histology report																X				
Follow-up CRF																	Х	Х	Х	X

In this chart Week 1 is the week in which cetuximab alone is given and Week 2 is the week in which radiotherapy is started.

Serious Adverse Event Forms, Patient Withdrawal Form and Death Form to be completed as needed.

Figure 11: Flowchart for assessments and CRF completion

10 Withdrawal of Patients

In consenting to the trial, patients are consenting to trial treatment, trial follow-up and data collection. If a patient wishes to withdraw from trial treatment, institutions should nevertheless explain the importance of remaining on trial follow-up, or failing this of allowing routine follow-up data to be used for trial purposes.

10.1 Withdrawal from Trial Treatment

A patient may stop trial treatment for the following reasons:

- Progression whilst on therapy
- o Unacceptable toxicity
- o Intercurrent illness which prevents further treatment
- o Withdrawal of consent for treatment by patient
- Any alterations in the patient's condition which justifies the discontinuation of treatment in the investigator's opinion.

The reason should be recorded on the Treatment CRF and Withdrawal form.

The patient should however remain in the trial for the purposes of follow-up and data analysis, therefore, patients who withdraw from trial treatment for any reason other than disease progression and withdrawal of consent from trial including data collection, will continue to be followed-up for disease progression and late toxicity.

On confirmed tumour progression, further formal follow-up within the trial ceases apart from ultimately recording date and cause of death of death.

10.2 Withdrawal of Consent

If a patient explicitly states their wish not to contribute further data to the study their decision must be respected and recorded on the Withdrawal form. Details should be recorded in the patient's hospital records and no further CRFs should be completed.

10.3 Moving

For patients moving from the area, every effort should be made for the patient to be followed up at another participating trial centre and for this new centre to take over the responsibility for the patient, or for follow-up via GP.

10.4 Lost to follow-up

If a patient is lost to follow-up every effort should be made to contact the patient's GP (if consented) to obtain information on the patient's status.

11 Data Handling

Please photocopy all completed CRFs, and retain the photocopy in the patient file at site. The original copy should be sent to the CTC.

Incoming forms will be checked for completeness, timeliness and compliance with the protocol prior to entry on database.

Any omissions in data should be noted on the CRFs. Regular data query requests and requests for any missing or outstanding will be made at intervals by the Data Manager. Any amendments to the CRFs must be initialled and dated by authorised personnel.

12 Confidentiality and Archiving

All information collected during the course of the trial will be kept strictly confidential. Information will be held on paper and electronically at the CTC. Both will comply with all aspects of the 1998 Data Protection Act.

All data collection forms will be coded with a trial number and will include two patient identifiers, usually the patient's initials and date of birth.

Any hospital reports received from the local sites must have personal details removed and identified using patient initials and trial number.

Consent from patients for access to their medical records by responsible individuals from the research staff or from regulatory authorities will be confirmed at site monitoring visits.

If a patient withdraws consent from further trial treatment but not from data collection, their data will remain on file and will be included in the final study analysis.

At the end of the trial, the CTC will archive securely all trial related documentation for 5 years. Arrangements for confidential destruction will then be made. Each local site must also retain trial documentation for 5 years.

If a patient withdraws consent for their data to be used, it will be confidentially destroyed immediately.

13 Statistical Considerations

If the results indicate that the R0 resection rate is consistent with a true rate of at least 75% then the proposed regimen is deemed worthy of further investigation in a future phase III trial. The R0 resection rate is about 50-60% in the intention-to-treat population using single agent fluoropyrimidine (5FU or capecitabine) as a radiation sensitiser - we use the midpoint of 55% in the sample size calculation. With the addition of irinotecan and cetuximab we expect this to increase to at least 75%. Using a Fleming's design with 80% power (and one-sided test of statistical significance at the 5% level), 35 patients would be required. Initially the recruitment target was 40 patients, which would allow for some drop-outs, this has been updated to 80 patients.

In the NWCOG-2 (RICE) trial and other studies of irinotecan-containing CRT regimes, diarrhoea is the most common serious toxicity. Within RICE 20% of 91 patients suffered grade 3 or 4 diarrhoea (all grade 3 apart from one grade 4). In the proposed study a true grade 3 or 4 diarrhoea rate of more than 30% would be unacceptable (as is standard for chemoradiation studies in pelvic cancers). We will monitor the number of grade 3 or 4 toxicities during the course of the trial. Given the original sample size of 40 patients, we would consider stopping the study early if 17 patients with a grade 3 or 4 diarrhoea were observed, since the probability of this occurring by chance if the true toxicity rate were 30% is 0.03.

Data on toxicity from the first 20 patients followed for at least one month following completion of CRT will be reviewed by an Independent Data Monitoring Committee (IDMC). This analysis, will be performed by the trial statistician and remain confidential to the IDMC. The IDMC will be asked to give advice on whether the trial should stop early because of unacceptable toxicities.

An analysis of the main outcomes will also be carried out, comparing the results of patients based on whether they are found to be KRAS wildtype or KRAS mutant.

The original proposal for EXCITE was based on seeing an increase in the R0 resection rate from 55% when using single agent fluoropyrimidine to 75% with the addition of irinotecan and cetuximab. This would have required 35 patients to achieve 80% power, using a Fleming's design, and the aim was to recruit 40 patients.

Since the planning of EXCITE, evidence has emerged that cetuximab is not effective in patients who have a KRAS mutant tumour (Lievre A, Bachet JB, Le Corre D, et al, Cancer EXCITE protocol v4.3; 21st August 2015

Res. 2006; and reviewed in Siena S, Sartore-Bianchi A, Di Nicolantonio F, et al, JNCI 2009). However as yet it is not known whether this would also be true when cetuximab is used in combination with radiotherapy as a radiation sensitiser, as is happening in EXCITE.

We are therefore proposing to increase the sample size of EXCITE from 40 to 80 patients. KRAS has been found to be mutated in 35-40% of colorectal adenocarcinomas (Barault L, Veyrie N, Jooste V, et al. Int J Cancer . 2008). Increasing the sample size to 80 patients would ensure that there are at least 40 K-RAS wild type tumours that can be analysed with respect to the R0 resection rate, as per the original design of the trial. Based on a 60% prevalence of wild type tumours, the chances of getting at least 40 such tumours from 80 patients are 97%. The increase in sample size is entirely due to having sufficient evidence to evaluate the effect of the planned treatment regimen on the R0 resection rate in K-RAS wild type tumours. This trial has not been powered to test for any significant differences between the patients with KRAS wild type and mutant tumours.

14 Trial Monitoring and Oversight

Participating sites and Principal Investigators must agree to allow trial-related on-site monitoring, Sponsor audits and regulatory inspections by providing direct access to source data/documents as required. Patients are informed of this in the patient information sheet and are asked to consent to their medical notes being reviewed by appropriate individuals on the consent form.

UCL CTC will determine the appropriate level and nature of monitoring required for the trial. Risk will be assessed on an ongoing basis and adjustments made accordingly.

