2.9 Proposed trial

The regimen of irinotecan and capecitabine used in addition to radiotherapy in a CRT regimen for downstaging locally advanced rectal cancer has been studied within the UK NWCOG-2 (RICE) trial. Within this trial the recommended phase II dose of radiotherapy at 45 Gy in 25 daily fractions, oral capecitabine at 650 mg/m² bd taken 7 days per week and

irinotecan at 60 mg/m² iv weeks 1,2,3 and 4 [Gollins '09], has now been used in 96 patients in the phase II element of the trial.

It is clearly of interest to study the effects of a biological agent on top of conventional chemotherapy as a radiation sensitiser. Cetuximab is the only agent of proven worth as a radiation sensitiser in a randomised trial, in the context of head and neck cancer [Bonner '06]. It may be the case that in the context of rectal cancer the triplet sensitising regime of capecitabine, irinotecan and cetuximab confers an additional advantage compared to capecitabine and irinotecan alone and could be included in a future phase III trial. It is also of interest to analyse the molecular markers KRAS and BRAF to determine their influence with regard to response in this context.

Data from 250 rectal cancer biopsies within the FOCUS trial ([name], personal communication) indicates that approximately 52% will be KRAS/BRAF wild type 45% KRAS mutant and 3% BRAF mutant (one patient was KRAS/BRAF mutant).

The current protocol EXCITE (NWCOG-4) examines this triplet combination. In view of the recognised acceptable but nevertheless significant grade 3 and 4 toxicity encountered in NWCOG-2 [Gollins '09], the current protocol keeps the doses of radiotherapy, capecitabine and irinotecan identical to NWCOG-2 but introduces a weekend break in the capecitabine schedule so that this is delivered five days per week from Monday to Friday only.

3 Selection of Clinicians

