5.1 Patient inclusion criteria

- Histologically confirmed rectal adenocarcinoma with lower (distal) limit ≤12 cm from the anal verge using rigid sigmoidoscopy
- Rectal Cancer staged with MRI as locally advanced:

Mesorectal fascia threatened (tumour ≤1mm from mesorectal fascia) Mesorectal fascia involved or breached

- Low tumours arising <5cm from the anal verge
- No evidence of metastatic disease
- No pre-existing condition which would deter radiotherapy, e.g. fistulas, severe ulcerative colitis (particularly patients currently taking sulphasalazine), Crohn's disease, prior adhesions
- Estimated GFR (using Cockroft-Gault formula) >50 ml/min. If this is less than 50ml/min a 24-hour urine collection for estimation of GFR is required or a serum EDTA clearance
- Absolute neutrophil count ≥ 1.5 x 10⁹/I. Platelets ≥ 100 x 10⁹/I, serum bilirubin <1.25 x upper limit of normal (ULN); serum transaminase(s) < 3 x ULN; serum ALP < 5 x ULN
- Fit to receive all study treatments
- Able to comply with oral medication
- WHO performance status 0 or 1
- Written informed consent

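### The 97% chance of at least 40 KRAS wild-type tumours rests on a colorectal prevalence that differs from the protocol's own rectal figure; on that figure it is 84%

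*Protocol*

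**What the plan says.** Section 13 (Statistical Considerations) explains why the sample size was doubled: "We are therefore proposing to increase the sample size of EXCITE from 40 to 80 patients". The purpose is to test the R0 resection rate in KRAS wild-type tumours with the numbers first planned for the whole trial. The protocol states that "Increasing the sample size to 80 patients would ensure that there are at least 40 K-RAS wild type tumours that can be analysed". The prevalence behind this is introduced with "KRAS has been found to be mutated in 35-40% of colorectal adenocarcinomas". From it the section takes 60% wild type, the cautious end of the implied 60–65%, and concludes: "Based on a 60% prevalence of wild type tumours, the chances of getting at least 40 such tumours from 80 patients are 97" per cent.

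Section 13 also says that the single-stage Fleming calculation (R0 rate 55% against 75%, one-sided 5%, 80% power) needs 35 patients, and that the target of 40 leaves room for drop-outs.

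Section 2.9 (Proposed trial) gives a different prevalence. It cites "Data from 250 rectal cancer biopsies within the FOCUS trial" and says that this source "indicates that approximately 52% will be KRAS/BRAF wild type 45% KRAS mutant and 3% BRAF mutant". Section 5.1 limits entry to one disease: "Histologically confirmed rectal adenocarcinoma with lower (distal) limit" at most 12 cm from the anal verge.

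**The concern.** The protocol holds two prevalences for the same quantity. The one specific to the trial's disease is in the background section. The more favourable and less specific one is in the sample-size justification. Section 13 neither mentions the rectal figure nor says why the colorectal one was preferred.

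The 97% is the only number offered in support of the step from 40 to 80 patients, and Section 13 attributes the whole increase to the wild-type evaluation. If the rectal figure is nearer the truth, the stated chance of reaching the wild-type target is too high, and the claim that 80 patients make it certain is further off. At stake is the accuracy of the stated justification, and possibly the power of the wild-type analysis. The second has to be checked before it is claimed.

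**Working it through.** **Inputs**
- Total sample size n = 80; target of at least 40 KRAS wild type (Section 13).
- Wild-type prevalence p = 0.60 (Section 13, from 35–40% mutant in colorectal cancer).
- Wild-type prevalence p = 1 − 0.45 = 0.55 (Section 2.9, rectal biopsies). As a check, 52% wild type for both genes plus 3% BRAF mutant also gives 55% KRAS wild type. The single double mutant that Section 2.9 mentions moves this by at most about 0.4 points.
- Patients required by the R0 test: 35 (Section 13).

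**Formula.** With X the number of KRAS wild-type tumours, X ~ Binomial(80, p), and the chance of reaching a count r is P(X ≥ r) = Σ C(80, k) p^k (1 − p)^(80−k), summed over k = r to 80.

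**Step 1: the protocol's own figures.** At p = 0.60, P(X ≥ 40) = 0.973, which reproduces the stated 97%. The 35 also reproduces: [(1.645·√(0.55·0.45) + 0.842·√(0.75·0.25)) / 0.20]² = 34.97.

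**Step 2: the rectal prevalence.**

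| | p = 0.60 | p = 0.55 |
|---|---|---|
| Expected wild type, 80p | 48 | 44 |
| P(X ≥ 40) | 0.973 | 0.844 |
| P(X < 40) | 0.027 | 0.156 |
| P(X ≥ 35) | 0.999 | 0.983 |

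For double mutants shifting p between 0.548 and 0.552, P(X ≥ 40) runs from 0.835 to 0.853, so the conclusion is unaffected. To keep a 97% chance of 40 at p = 0.55, 88 patients would be needed.

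**Step 3: the effect on power.** For each wild-type count k, take the exact one-sided 5% binomial test of 0.55 and its power at 0.75, then average over X ~ Binomial(80, p): Σ P(X = k) × power(k). The result is 0.872 at p = 0.60 and 0.838 at p = 0.55. Both exceed the planned 0.80.

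**Step 4: uncertainty in the 55%.** Treating 250 biopsies as a simple random sample (an assumption), the standard error is √(0.55·0.45/250) = 0.0315, so the 95% interval is 0.55 ± 1.96·0.0315, about 0.49 to 0.61. Over that interval P(X ≥ 40) runs from about 0.46 to 0.98.

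**Step 5: incomplete typing or evaluability.** Both probabilities treat all 80 patients as yielding an analysable KRAS result. The protocol gives no failure rate. As an assumption for illustration only, 76 evaluable patients (5% lost) would give P(X ≥ 40) = 0.92 at p = 0.60 and 0.70 at p = 0.55.

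**The case against.** The strongest reply has three parts, and much of it stands.

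First, nothing was miscalculated. Section 13 discloses its input and the 97% follows from it. That is right: the fault is an unreconciled assumption.

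Second, 55% is not established as the true value. Section 2.9 calls it approximate and attributes it to a personal communication, whereas the 35–40% mutant figure carries a published citation and 60% is its cautious end. The simple interval around 55% just includes 60%. This stands too, and it is why a range is the right correction, not a swap of one single value for another. It does not justify silence, because 55% is the only figure in the protocol specific to the disease being treated.

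Third, 40 is a padded target. A reader might infer from the sixfold rise in the chance of missing it (15.6% against 2.7%) that the wild-type analysis is underpowered or that more patients must be recruited. The documents do not support that: the requirement is 35, which is reached with 98% probability at 55%, and averaged power stays above 80%.

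Two further inferences should be resisted. One is to find the smallest number with exact power of 80%, which is 37, and quote the 95% chance of at least 37 as the chance of adequate power. Exact power is saw-toothed: 80.6% at 37, 77.7% at 38, 74.7% at 39, 82.1% at 40. The chance of landing on a count with at least 80% exact power is about 80% at a prevalence of 55%. Averaged power is the sounder summary. The other is to use 52% as the prevalence. That figure is for tumours wild type in both KRAS and BRAF, and the target in Section 13 is KRAS wild type alone.

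**Conclusion.** The point holds as a minor inconsistency. Section 13 rests its probability on a colorectal prevalence that disagrees with the rectal prevalence in Section 2.9, and does not explain the choice. On the rectal figure, the chance of at least 40 wild-type tumours is 84% rather than 97%, the expected count is 44 rather than 48, and the chance of falling short is about 16% rather than 3%. On neither figure do 80 patients guarantee 40.

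The consequence is confined to the stated justification. Sample size, test and planned power survive. These results assume independent patients, a KRAS result for everyone, and a prevalence of 55% that is itself uncertain.

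**What to change.** Amend two or three sentences of Section 13:
- Cite the rectal figure from Section 2.9 beside the colorectal one and give the probability of at least 40 wild-type tumours as a range: 84% at 55% (44 expected) and 97% at 60% (48 expected). If 60% is kept as the planning value, say why it is preferred to the rectal data.
- Replace the wording that 80 patients will ensure 40 with a statement that 40 is likely.
- Add that, at 55%, the chance of at least the required 35 is about 98% and exact power averaged over the wild-type count is about 84%, so the total of 80 stands.
- If an allowance for failed typing or non-evaluable patients is quoted, label it an assumption.

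The cost is a less favourable stated probability. No change to recruitment, analysis or conduct follows.

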14.1 On-site monitoring

The degree of on-site monitoring will be proportionate to the objective, purpose, phase, design, size, complexity, blinding, endpoints and risks associated with the clinical trial.

Sites will be sent a letter in advance confirming when a routine monitoring visit is due. The letter will include a list of the documents that are to be reviewed, interviews that will be conducted, planned inspections of the facilities, who will be performing the visit and when the visit is likely to occur.

The Trial Coordinator will visit high recruiting sites at least once over the duration of the trial, as documented in the trial monitoring plan.

The purpose of these visits is to:

- Verify that the rights and well-being of patients/participants are protected
- Verify accuracy, completion and validity of reported trial data from the source documents.
- Evaluate the conduct of the trial within the institution with regard to compliance with the currently approved protocol, GCP and with the applicable regulatory requirements.

As detailed in the trial Monitoring Plan, the following checks will be undertaken for a proportion of patients:

• Source Data Verification of patient informed consent, □ eligibility, safety reporting and capturing of trial endpoints.

- Review of the Investigator Site File for filing of essential documents
- Visit pharmacy to perform checks on drug accountability, drug storage, temperature recording and filing of essential documentation.

Monitoring report

Following a monitoring visit, the Trial Coordinator will provide a report to the site, which will summarise the documents reviewed and a statement of findings, deviations, deficiencies, conclusions, actions taken and actions required. The Principal Investigator at each site will be responsible for ensuring that monitoring findings are addressed (this may be delegated to an appropriate member of staff).

14.2 Central monitoring

Data stored at UCL CTC will be checked for missing or unusual values (range checks) and checked for consistency over time. If any problems are identified data queries will be issued to the site. Sites are required to resolve any queries and update the relevant CRF as required. All changes must be initialled and dated. The amended version must be sent to UCL CTC and a copy retained at site.

Sites will also be requested to submit screening logs and staff delegation logs to UCL CTC on request and these will be checked for consistency and completeness.

Copies of completed drug accountability logs will be collected at UCL CTC for all trial patients. Sites will be required to submit logs following the patient's completion of trial treatment or on request. At least 10% of the logs from each site, always including the log for the first patient enrolled at site, will be monitored centrally (unless already conducted at an on-site visit) to ensure completeness and correlation with data collected in the CRF.

Sites will be requested to conduct quality control checks of documentation held within the Investigator Site File and Pharmacy Site File at the frequency detailed in the trial monitoring plan. Checklists detailing the current version/date of version controlled documents will be provided for this purpose.

Where central monitoring of data and/or documentation submitted by sites indicates that a patient may have been placed at risk (e.g. evidence of an overdose having been administered, indication that dose modifications for an IMP were not observed following an

adverse reaction, etc.), the matter will be raised urgently with site staff and escalated as appropriate (refer to section 14.4 ('For cause' on-site monitoring) and 16 (Incident Reporting and Serious Breaches) for further details).

14.3 'For cause' on-site monitoring

Additional on-site monitoring visits may be scheduled where there is evidence or suspicion of non-compliance at a site with important aspect(s) of the trial/GCP requirements. Sites will be sent a letter in advance outlining the reason(s) for the visit. The letter will include a list of the documents that are to be reviewed, interviews that will be conducted, planned inspections of the facilities, who will be performing the visit and when the visit is likely to occur.

15 Pharmacovigilance

